**Managing Distress in Malignant Brain Cancer – Patients with Brain Metastases**  
**Approval: 1/7/2022**

## SIGNIFICANCE

Brain tumors originate either in the brain itself (primary brain tumor, PBT) or develop secondarily to another cancer that has spread to the brain (brain metastasis, bMET). bMET is much more common than PBT, with 10-30% of all cancers spreading to the brain (1). At least 170,000 Americans will be diagnosed with bMET each year (1, 2)—nearly double the incidence rate of PBT—and this figure is likely an underestimate (3). The symptoms associated with brain cancer are numerous and include fatigue, sleep disturbance, headache, nausea, seizure, cognitive changes, and neurologic symptoms, such as dizziness, difficulty with balance, sensory problems, and numbness/tingling. Most patients endorse multiple symptoms of at least moderate severity (5), and the vast majority require some form of rehabilitation therapy (6). Compared to other cancer populations, individuals with brain cancer are less likely to be employed (7, 8) and more likely to be divorced (9). Activities of daily living that promote independence, such as self-care, locomotion/mobility, and driving can be affected by the tumor itself, treatment, or both (10, 11).

**Military service members and Veterans are a particularly vulnerable group and may be at increased risk for brain cancer.** Brain cancer is the third most common cause of cancer death among active-duty service members (SMs) in the US military (12). Although PBT accounts for less than 1% of all cancers treated in the US Veterans Affairs Health Care System (VA) (13), evidence suggests that individuals with a history of military service are at elevated risk for PBT compared to other occupations, because of combat, exposure to electromagnetic fields / radiation (14, 15), or toxic agents during chemical warfare (16, 17). Further, with respect to bMET, the most frequently diagnosed cancers in the VA are those most likely to result in bMET: lung, colon, kidney, and melanoma (4). Despite this increased risk, Veterans who receive VA care for brain cancer may experience more favorable mortality outcomes compared to the general population: In a matched case analysis, SMs with PBT demonstrated a survival advantage across age, race, histological, and treatment history strata compared to civilians with PBT (18). Taken together, these data suggest that while military populations may be at greater risk of developing brain cancer, they may also experience longer survival periods—making preservation of life quality particularly important among SMs and Veterans with brain cancer. Of particular relevance to military populations is the finding that a brain cancer diagnosis is associated with increased risk of posttraumatic stress disorder (PTSD) and suicide in the first year following treatment (19). Up to 67% of Veterans with cancer report symptoms of PTSD brought on by their experience with cancer (20) and since 2008, the number of Veterans with completed suicides have exceeded 6,000 annually; an average rate of 16-20 per day, respectively (21). Depression, PTSD, and substance dependence are all major risk factors for suicide in Veterans (22-24). Importantly, all of these factors have been shown to be improved by behavioral health interventions (25-27), including in patients with advanced cancer (25, 26).

**Treatment options for individuals with brain cancer are lacking.** Medical advances have nearly doubled median survival rates over the past decade (28, 29). However, there is still no cure for malignant brain cancer. The median overall survival for patients with bMET is now approximately 6 months, with 1- and 2-year survival rates at 8.3% and 1.4%, respectively (30). Medical interventions targeting amelioration of PBT and bMET are associated with a range of adverse effects, including cognitive decline and fatigue, compounding the symptoms of the disease itself. Given this poor prognosis, medical management often focuses on symptom alleviation (e.g., the provision of steroids to reduce brain swelling, anticonvulsants to reduce seizure frequency) (31). Tailored, evidence-based behavioral health interventions for SMs, Veterans, their beneficiaries, and civilians with brain cancer that focus on preparation for living with a brain tumor, its treatment, and the fatal disease trajectory are not only essential for mission readiness, but are also mission critical.

**Brain cancer is associated with significant distress and reduced quality of life.** In the absence of curative medical treatments for malignant PBT and bMET, care must include a focus on increasing psychological preparedness and improving quality of life. Nearly all patients with PBT (93%-95%) report symptoms of depression (32, 33), with rates of clinical diagnoses greater than both other oncology populations and the general population (22%- 41% v. 13% v. 7%, respectively) (33-38). Our own preliminary data demonstrate that those with PBT endorse a particular type of distress—death anxiety—at a drastically higher rate than other cancer populations (81% v. 32%) (39). Death anxiety refers to fear and preoccupation with thoughts of death and dying that may interfere with individuals' daily functioning. Anxiety regarding death is understandable among those with brain cancer given the uncertain disease trajectory, lack of curative treatment, potential loss of functioning, and the inherent existential nature of brain cancer itself (40). In advanced cancer patients, behavioral health interventions that focus on increasing preparedness, finding meaning, and understanding disease trajectory have been shown to reduce distress, and improve mood and life quality (25).

[figure not shown]
**Individuals with brain cancer are significantly underrepresented—and often excluded—from behavioral health**

**intervention trials that could improve their preparedness and life quality.** Despite documented high rates of distress among those with PBT and bMET, little is known about the trajectory of this distress, its correlates, or effective treatments. Our research team recently conducted a systematic review of the extent to which individuals with brain cancer are included in psycho-oncology research focused on death-related distress. Results revealed that this patient population represented only 0.18% of participants included in such studies (41). Frequently, this omission is not due to oversight, but rather is a specific exclusion criterion at least partly based on the unsubstantiated assumption that individuals with brain cancer are not cognitively capable of participating in such research (41). While individuals with PBT and bMET are at risk for cognitive decline, only a small sub-sample demonstrate cognitive impairment to an extent that would exclude them from participating in intervention trials. In our own research, we found that the vast majority (91%) of patients with PBT were cognitively eligible (66% fully functional, 25% with mild cognitive impairment) and only 9% performed in an ineligible range reflective of dementia (42). In short, the need to include SMs, Veterans, their beneficiaries and civilians with PBT and bMET in behavioral health intervention research is clear, and their exclusion represents an injustice that sustains a critical gap in clinical knowledge and services for those who are most in need of support.

### Study Treatment/ Behavioral Health Intervention.

An evidence-based, effective intervention to address distress in advanced cancer exists but has never been studied in SMs, Veterans, their beneficiaries or civilians with brain cancer. Though cognitive behavioral therapy is effective for a variety of psycho-oncology concerns, it is not effective for treating depression and related symptoms in individuals with advanced cancer (43-46). Similarly, psychopharmacological approaches are of limited benefit and are contraindicated for individuals with PBT or bMET; antidepressant use is associated with lowered seizure thresholds, cognitive decline, worsened fatigue and tumor recurrence (47, 48).

An alternative intervention, **Managing Cancer and Living Meaningfully (CALM)**, was designed to specifically address the inevitable challenges patients with advanced cancer face. CALM is a brief, individual, manualized, behavioral health intervention developed by palliative care and psycho-oncology leaders to provide hope, manage distress, increase preparedness, and improve quality of life (25, 49, 50). CALM optimally consists of six individual sessions of 45 to 60 minutes, delivered over a three- to six-month period. CALM sessions address four broad and interrelated domains found to be important and relevant in this population: (1) symptom management and communication with healthcare providers, (2) changes in personal relationships, (3) sense of meaning and purpose, and (4) the future, hope and mortality (Figure 1). These domains are addressed with all patients at some point during the intervention, although the sequence and relative emphasis on each domain vary, depending on their urgency and relative importance to each individual participant. CALM research conducted over the past decade has shown CALM to be feasible and acceptable (51-53), and a large recent RCT has shown that CALM is effective in treating and preventing depression at 3 and 6 months compared with usual care (25). Notably, CALM is the only intervention shown to significantly decrease death anxiety (54). No adverse events were reported during the RCT, including increased risk for suicide. However, previous studies have not targeted SMs, Veterans, their beneficiaries or civilians with brain cancer during CALM trials.

**Figure 1.** Domains of Calm

### Primary Outcomes

1. Assess the Need for Adaptations to the CALM Intervention as Measured by the Applicability of the 4 CALM Domains
2. Feasibility of CALM Intervention in the Proof of Concept Project as Measured by the Rates of Participant Screening, Eligibility, and Consent.
3. Feasibility of CALM Intervention in the Proof of Concept Project as Measured by Attendance at CALM Sessions
4. Feasibility of CALM Intervention in the Proof of Concept Project as Measured by the Rates of Post-session Assessment

## Completion

5. Feasibility of CALM Intervention in the Proof of Concept Project as Measured by Post-Intervention Assessment Completion
6. Benefit of Intervention in the Proof of Concept Project as Measured by Participant Responses to Researcher-developed Questions as Part of the Exit Interview

## Primary Endpoints

1. Rate of domains applicability
2. % of participant Screening, Eligibility, and Consent
3. % of attendance at CALM Sessions
4. % of post-session assessment completion
5. % of post-intervention assessment completion
6. Rate of intervention benefit

## RESEARCH STRATEGY AND FEASIBILITY

**Approach.** A mixed-methods approach, utilizing the NIH Science of Behavior Change (SOBC) supported ORBIT model has been chosen for this study. The ORBIT model begins with a theory grounded in behavioral science about the mechanisms of behavior change (Phase I), and develops an intervention in small incremental steps, paying attention to tailoring, acceptability, and testing efficacy of early outcomes using smaller experiments (Phase II), before embarking on a randomized controlled trial (Phase III).

**Study Population.** Adult patients with brain metastases diagnosis.

**Inclusion Criteria.** This study will consider for enrollment individuals of all genders, ethnic, racial, and socioeconomic backgrounds. Participants must: (1) have a confirmed brain met diagnosis via medical records, (2) be a minimum of 2 weeks post-surgical cranial resection or biopsy (if applicable), (3) be primarily English speaking, (4) be age 18+, (5) obtain  $\geq 20$  on Telephone Interview for Cognitive Status, (6) have current elevated depression (Patient Health Questionnaire-9 Item [PHQ9]  $\geq 10$ ) or death anxiety symptoms (Death and Dying Distress Scale [DADDS]  $\geq 15$ ), and (6) have reliable internet connection.

**Exclusion Criteria.** This study will exclude participants with: (1) Major communication difficulties as determined by the research team which would prohibit psychotherapeutic interaction, (2) inability to meet with interventionist via an electronic device for telehealth intervention sessions, or (3) inability to provide informed consent.

[figure not shown]
**VCU Recruitment.** VCUHealth treats approximately 400 individuals with bMET annually. Participants can be directly referred by their neuro-oncology clinical team. Flyers will also be email or mailed to those seen within VCUHealth in the last year. If patients are interested in participating, a telehealth screening interview will be scheduled. Trained study staff will screen for eligibility. If eligible, individuals will have the study described to them. Interested individuals will be emailed and asked to read the consent form and encouraged to ask any questions. They will be informed that their decision to (or not) participate will not affect their care at any VCU facility. Once all questions are answered, interested individuals will be asked to sign the consent form electronically.

**Scientific Rigor.** To parallel the multi-phase drug development scientific process, including intervention development and dose-response testing (Phase I), feasibility and acceptability evaluations (Phase II), and eventual Phase III efficacy trials, the NIH SOBC ORBIT model was selected to guide this project. To promote a robust and unbiased approach, we will: (1) use validated measures, (2) have a non-clinical research assistant (RA) conduct eligibility screening and consent to reduce coercion, and (3) have the RA collect participant measures and conduct exit interviews.

**AIM 1: Proof-of-Concept Trial Design.** Using the ORBIT model, we will initially conduct a 1-year Phase IIa/b *Proof-of-Concept Trial* to guide CALM implementation for individuals with PBT. Within two weeks before and after the intervention and 3 months post-intervention, participants will be asked to complete self-report surveys of behavioral and psychological variables

via a secure online data collection system (REDCap). Participants will be offered a \$20 gift card for completing these surveys across each of the 3 timepoints (pre-intervention, post-intervention, follow-up). If paper copies of the questionnaire are preferred by the participant, these can be mailed and the RA will input any data into REDCap upon return. Six sessions of CALM therapy will be provided at no cost to participants. After each intervention session, participants will be sent a link for a brief post-session satisfaction survey via secure email link. Participants will rate 1) topic applicability; 2) perceived benefit of session; 3) comfort with interventionist(s); and 4) overall satisfaction. Participants who withdraw will be contacted and asked open-ended questions on reasons for termination and suggestions for improvement.

Within one month of intervention completion, the RA will conduct individual exit interviews by phone, which will be audio recorded for verbatim transcription. Interviews will assess length and number of sessions, content applicability, recommended modifications, helpful and unhelpful aspects of sessions, perceived benefits, overall satisfaction, and suggestions for improvement. This will inform treatment preferences, intervention adaptations, and overall satisfaction. Our team has used these survey and interview measures with success in prior treatment development trials. At any time during the intervention, participants considered by the therapist to be at acute risk for suicide, or who demonstrate significant worsening of depression or other psychiatric co-morbidities that require treatment, will be referred for psychiatric assessment and treatment in the Department of Psychiatry. This may include pharmacotherapy or other psychiatric interventions.

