### Evaluation Metrics

Domain	Metric	Target
Recruitment	• Screening rate	70%
Feasibility	• Eligibility rate	50%
	• Reasons for ineligibility	--
	• Enrollment rate	30%
Acceptability of Procedures	• Baseline questionnaire adherence	75%
	• Post-session survey adherence	60%
	• Post-CALM questionnaire adherence	60%
	• Exit interview adherence	60%
Intervention Acceptability	• Intervention Completion of Trial Initiators	70%
	• Reason for withdrawal	--
	• Intervention satisfaction survey benefit rating	Rating $\geq$ 4/5
	• CEQ rating (preliminary)	$\geq$ 14

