### Psychological Distress and Life Quality Outcome Measures

Measure	Items	Distress Descriptors
Patient Health Questionnaire	PHQ-9	9 0-5 5-9 10-14 15-19 20-27 Minimal Mild Moderate Moderately Severe Severe
Death and Dying Distress Scale	DADDS	15 0-24 25-46 47-75 Low Moderate Severe
Generalized Anxiety Disorder	GAD-7	7 0-4 Minimal

			5-9	Mild
			10-14	Moderate
			15-21	Severe
Quality of Life at the End-of-Life Cancer Scale	QUAL-EC	17	0-68	--
Functional Assessment of Chronic Illness Therapy – Spiritual Wellbeing Scale	FACIT-sp	12	0-48	--
Fear of Cancer Recurrence	FCR-7	7	$\geq 17$ $\geq 27$	60 th percentile 90 th percentile
Post-Traumatic Stress Disorder Checklist	PCL-5	20	$\geq 31$	Probable PTSD
Suicidal Ideation	PHQ-9	1	0-3	--
Tobacco, Alcohol, Prescription medication and other Substance Use	TAPS	4	0 1 2	No Use Problem Use Higher Risk

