## DATA ANALYSIS.

Detailed records of the number of individuals who screen, are eligible, enroll, complete assessment measures, and attend telehealth sessions will be kept. Reasons for attrition will be recorded. Individuals who “no-show” will be contacted to assess continued interest and will be rescheduled as appropriate. Each attempt to contact participants will be recorded. This information will guide future recruitment/retention and inform feasibility. Recruitment source will be tracked to determine the most fruitful strategies. We will calculate frequencies and proportions to explore preliminary feasibility outcomes and means and standard deviations or medians and interquartile ranges to assess preliminary acceptability. The two-sample t- tests and/or Mann-Whitney U-test, and chi-square tests will be used to compare eligible patients who did and did not enroll in terms of demographic, medical, and psychiatric variables. Within-group changes in behavioral and psychological variables will be explored to prepare for future pilot and efficacy trials. Thus, for each data collection time points we will calculate the mean and standard deviation of exploratory outcomes. In addition, we will calculate the correlation on the measures between time points as well as calculating the difference scores and the accompanying standard deviations.

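### Does admitting patients on a DADDS score of 15 or more, inside the band the outcome table labels Low, call for a change to the plan?

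*Combined protocol and SAP*

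**What the plan says.** Under Research Strategy and Feasibility, the first of the two inclusion criteria numbered 6 is an either-or rule. A patient must "have current elevated depression (Patient Health Questionnaire-9 Item [PHQ9] $\geq 10", "or death anxiety symptoms (Death and Dying Distress Scale [DADDS] $\geq 15". The criterion carries a superscript reference (23), and the reference list is not in the supplied text.

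The table of Psychological Distress and Life Quality Outcome Measures gives item counts, score ranges and descriptors. Its DADDS row reads "15 0-24 25-46 47-75 Low Moderate Severe" and its PHQ-9 row reads "9 0-5 5-9 10-14 15-19 20-27 Minimal Mild Moderate Moderately Severe Severe".

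Two planned outputs depend on who is admitted. The second primary endpoint is the percentage "of participant Screening, Eligibility, and Consent", and Evaluation Metrics sets a 50% target for the "Eligibility rate". The Data Analysis section adds exploratory summaries: "Within-group changes in behavioral and psychological variables will be explored to prepare for future pilot and efficacy trials".

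**The concern.** The criterion can be read as requiring elevated symptoms on either scale, yet part of the qualifying DADDS range carries the label Low in the same protocol. The two halves of the rule also follow different standards: the PHQ-9 cut coincides with the start of Moderate, while the DADDS cut lies 10 points below it. A patient with PHQ-9 of 9 or less and DADDS of 15 to 24 therefore enters although neither entry scale reaches Moderate.

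Two things could be at stake. A reader applying the table's labels might take the eligibility rate for the share of patients with at least moderate distress. And the DADDS change scores, standard deviations and between-visit correlations would include patients who can improve by at most 24 DADDS points and 9 PHQ-9 points, which could make them a poor guide for a later trial with a different entry cut.

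**Working it through.** **Reading the table row.** The DADDS row is run together in the text. Fifteen items with a maximum of 75 gives 75/15 = 5 points per item, and the bands hold 25 + 22 + 29 = 76 scores, covering 0 to 75 without gap or overlap. So 15 in that row is the item count, and Low is 0 to 24.

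**Counting scores.** Scores 15 to 24 both qualify and are labelled Low: 10/25 = 40% of the Low band, and 10/61 = 16% of the qualifying scores 15 to 75. These count possible scores, not patients.

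**Possible share of patients.** The documents give no DADDS distribution, so these inputs are assumptions:

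- DADDS: normal, restricted to 0 to 75 with half-point continuity correction, mean μ of 20, 25, 30 or 35 and SD σ of 12, 15 or 18.
- PHQ-9 of 10 or more: p = 0.22 or 0.41. The Significance section gives 22% to 41% for primary brain tumours, "with rates of clinical diagnoses greater than both other oncology populations and the general population"; this is a stand-in, from a different tumour population and for diagnoses rather than a PHQ-9 cut.

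That makes 4 × 3 × 2 = 24 combinations. With the scales independent:

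- P(DADDS ≥ c) = [Φ((75.5 − μ)/σ) − Φ((c − 0.5 − μ)/σ)] / [Φ((75.5 − μ)/σ) − Φ((−0.5 − μ)/σ)]
- Share meeting the criterion: E(c) = p + (1 − p) × P(DADDS ≥ c)
- Share of qualifiers entering only through 15 to 24: [E(15) − E(25)] / E(15)

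The value 25 is used only because it is the table's Low/Moderate boundary.

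Worked example, μ = 20, σ = 12, p = 0.22:

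- P(≥15) = 0.7076 and P(≥25) = 0.3700
- E(15) = 0.22 + 0.78 × 0.7076 = 0.772
- E(25) = 0.22 + 0.78 × 0.3700 = 0.509
- Difference 0.263; share entering only by this route 0.263/0.772 = 0.341

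| Quantity, independent scales | Range over 24 combinations |
|---|---|
| E(15) | 0.769 to 0.975 |
| E(25) | 0.509 to 0.888 |
| Difference | 0.087 to 0.263 |
| Share entering only through 15 to 24 | 0.089 to 0.341 |

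With correlation of 0.3 to 0.7 between the scales (Gaussian copula), the difference is 0.108 to 0.295 and the share 0.111 to 0.414. E(25) then falls below 50% in 1, 2 and 3 of the 24 combinations at correlations 0.3, 0.5 and 0.7, with a minimum of 0.418. None of these is an eligibility rate, which also depends on cognition, language, internet access and the remaining criteria. They say nothing firm about the 50% target.

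**Would a split by entry route help?** Patients with PHQ-9 of 10 or more and DADDS below 25 also have little room to fall on the DADDS, and they qualify whatever the DADDS cut. Their share of qualifiers is p × [1 − P(≥25)] / E(15). At μ = 20, σ = 12, p = 0.41 this is 0.41 × 0.630/0.8275 = 0.312; the range over the 24 combinations is 4% to 31%. A split isolating DADDS 15 to 24 with PHQ-9 below 10 leaves them in the comparison group.

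**Precision in a small subgroup.** The 95% limits for an SD, as multiples of the estimate, are √[(n − 1)/χ²] at the 0.975 and 0.025 quantiles on n − 1 degrees of freedom: 0.66 to 2.04 for n = 8 and 0.76 to 1.46 for n = 20. The plan states no sample size; these n are illustrations.

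**The case for a change.** The strongest case for a change is that the conflict is in the text and needs no modelling. The table is the protocol's only stated interpretation of DADDS scores, its PHQ-9 row shows what a matching cut looks like, and the rule feeds a primary feasibility endpoint. One sentence and one extra summary would cost almost nothing.

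The mismatch and the missing explanation stand. The rest does not carry a change. An entry criterion asks who might benefit; a descriptor column says how to talk about a score, and the two need not share a boundary. The word for elevated stands next to depression, and carrying it over to death anxiety is the natural reading but not the only one. The protocol's account of earlier CALM evidence covers prevention of depression as well as treatment, so admitting patients below Moderate fits the rationale, although that does not explain the value 15. The cited reference may do so; it cannot be checked here.

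The suggested split is also weak in itself. An eligibility rate within a group defined by having qualified has no meaning; only that group's share of eligible patients does. And, as shown above, limited room to fall on the DADDS comes partly from the either-or rule, whatever the DADDS cut.

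**Conclusion.** No change is needed. The entry cut and the Low label do not line up, and 10 scores fall in the overlap, but the documents do not show that either figure is wrong. Followed as written, the plan gives an eligibility rate that is correct for its own criterion, and nothing in it presents that rate as the share with moderate distress. The change scores, SDs and correlations are descriptive and correctly describe the admitted population; no sample size or error rate rests on the DADDS cut.

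What remains is a gap that analysts and readers can fill: state the criterion beside the eligibility rate and show the baseline DADDS distribution. Anyone planning a later trial with another cut can summarise DADDS change by baseline band (0 to 24 against 25 and over), whatever the entry route, from scores the study already collects. The sponsor may wish to add a sentence explaining why a score in the Low band qualifies, or to reconcile the criterion and the table; that is a matter of clarity.

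The 9% to 34% of qualifiers entering only by this route (11% to 41% with correlated scales) rests wholly on assumed DADDS distributions and a stand-in depression rate. The conclusion does not depend on it.

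### The written suicide-risk referral rule stops when the CALM sessions stop, but the PHQ-9 ideation item appears to be collected again at the post-intervention and 3-month surveys

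*Combined protocol and SAP*

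**What the plan says.** The combined protocol and SAP has one referral rule, in the AIM 1 text of Research Strategy and Feasibility, directly after the exit interview. It begins "At any time during the intervention, participants considered by the therapist to be at acute risk for suicide". The same sentence adds people whose depression or other psychiatric illness worsens enough to need treatment. Both groups are referred for psychiatric assessment and care.

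The same part of the plan sets the survey schedule: "Within two weeks before and after the intervention and 3 months post-intervention, participants will be asked to complete self-report surveys". Surveys are completed in REDCap. If a participant prefers paper, "these can be mailed and the RA will input any data into REDCap upon return".

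The Psychological Distress and Life Quality Outcome Measures table lists the PHQ-9 and, in a separate row, suicidal ideation as a single PHQ-9 item scored 0 to 3. That row gives no descriptor and no action threshold. Data Analysis plans means and standard deviations of the exploratory outcomes at each collection point, with correlations and difference scores between points.

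On staffing, Scientific Rigor says the team will "have a non-clinical research assistant (RA) conduct eligibility screening and consent to reduce coercion" and will "have the RA collect participant measures and conduct exit interviews".

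**The concern.** The referral rule is tied to the period in which a therapist is seeing the participant, yet the plan asks about suicidal thoughts after that period. At the two later surveys the recipient is a database or a research assistant, and nothing in the available text says that a clinician sees the answer, how soon, or what follows.

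The population makes this matter. People qualify with a PHQ-9 of at least 10 or a DADDS of at least 15, so the trial selects for depression or death anxiety. Significance links a brain cancer diagnosis to raised suicide risk in the first year after treatment (cancer treatment, not CALM). At stake is the safety of participants who report ideation once their sessions are over.

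**Working it through.** There is no figure to reproduce. The check compares the rule's window with each point at which ideation might be recorded or risk disclosed.

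1. **What the window covers.** AIM 1 uses the word intervention for the CALM sessions. It places surveys before and after the intervention and 3 months later, and it times the exit interview from intervention completion. On the plan's own usage, those contacts lie outside the window.

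2. **Other rules.** The remaining mentions of suicide are background risk, the absence of adverse events in the earlier CALM randomised trial, and the ideation row in the measures table. Data Analysis describes group summaries and tracking of attrition, with no review of individual answers.

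3. **Where the ideation item is collected.** No sentence lists the contents of the surveys. AIM 1 describes them as covering behavioral and psychological variables, the measures table lists such measures including the ideation item, and Data Analysis summarises exploratory outcomes at each time point. Together these support the inference that the item is in all three surveys. The survey sent after each session covers only topic applicability, benefit, comfort with the interventionist and satisfaction, so it does not ask about ideation.

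4. **Each point against the rule.**
   - *Screening.* Outside the window. Use of the PHQ-9 here is inferred from the eligibility criterion, and a DADDS score alone could qualify someone. It is a live telehealth interview by trained staff, so the gap is smaller.
   - *Pre-intervention survey.* Outside the window, but within two weeks before CALM begins. Those who start then see a therapist and come under the rule, so the gap is smaller.
   - *During sessions.* Covered, through the therapist.
   - *Post-intervention survey.* Outside the window, within two weeks after the intervention, with no later therapist contact described.
   - *3-month survey.* Outside the window, again with no therapist contact described.
   - *Exit interview and withdrawal contact.* Neither is described as collecting the ideation item. Exit interviews are calls by the research assistant. For withdrawals the plan says only: "Participants who withdraw will be contacted and asked open-ended questions on reasons for termination" and for suggestions. Risk might be disclosed in either, and no referral path is stated.

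The main gap is therefore at the post-intervention and 3-month surveys.

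**The case against.** The strongest reply is that silence is weak evidence in a short document whose consent pages were removed before review. Those pages may describe what happens after a positive answer, and staff may act on one whatever the protocol says. This stands as a limit: a reader might infer that positive answers would go unanswered or that the trial has no wider safety plan, and the documents support neither. It does not remove the point, because the rule that is written down has a window, and that window excludes the later surveys.

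A second reply is that the collection points are not alike. That is right. A reader might infer that every PHQ-9 collection is equally unprotected, but live screening and the therapist contact that follows the pre-intervention survey make those gaps smaller. Nor should the exit and withdrawal contacts be counted as ideation measurements.

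A reader might also try to size the gap from the feasibility targets for completion and eligibility. Those targets do not measure it. Non-completion will include death and medical decline in a population with a median survival of about 6 months. Screening failures include people excluded on cognition, language or internet access, and anyone who fails the symptom criterion is below both cut-offs.

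Finally, the earlier CALM trial reported no adverse events, including no increased suicide risk, and recruits come from people already in clinical contact. Both facts are reassuring about background safety. Neither says who acts on an answer given after sessions end.

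**Conclusion.** The point holds for the post-intervention and 3-month surveys. Followed as written, the referral rule is not triggered by a positive ideation answer, or by marked worsening of depression, reported there. This is more than missing detail: a stated rule has a window that leaves out the points at which ideation is measured after therapist contact ends.

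The conclusion rests on two assumptions: that the ideation item is in those surveys, which is a strong inference but not stated, and that intervention means the CALM sessions, as AIM 1 uses it. Confidence is moderate because the consent pages are not available.

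The documents give no rate of positive ideation answers, so the number of people affected cannot be estimated. The matter is one of participant safety; no endpoint, estimate or error rate changes. It should be fixed.

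**What to change.** Amend the referral rule in AIM 1 so that the existing psychiatric referral runs through the 3-month survey. Name an existing study clinician or therapist to review the ideation item when each PHQ-9 is submitted online or received by mail. Give the non-clinical research assistant a written escalation path to the same referral for any risk disclosed at screening, exit interview or withdrawal contact. Screening comes before consent, so its script would need a line on escalation.

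The cost is protocol wording and some clinician time for about three months after each participant's last session. Mailed forms can be reviewed only on receipt, so some delay remains for them. No new visits, measures or staff are needed.
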